9 TREATMENT OF SUBJECTS

9.1 Investigational Products

9.1.1 Treatment Regimens

FOL-005 solution and placebo of FOL-005 solution will be administered at the trial centre. The solutions are intended for local intradermal injection into the skin. With each injection a volume of 50µl will be administered. The treatment areas will have a dot tattoo in the centre, edges will be drawn as dots with a skin marker, maximum once per week (Figure 2).

Each subject will have 2 treatment areas, A and B, evenly located on the scalp, at least 5 cm apart from each other. Treatment areas will be treated with either of the following treatments: $0.00625 \ \mu g$, $0.025 \ \mu g$, $0.050 \ \mu g$, $0.100 \ \mu g$ and placebo according to the randomisation schedule.

Figure 2 Treatment areas

Treatment areas will be on the balding scalp. Treatment sites have to be free of scars, tattoos or dermatological defects that might impair measurements. Treatment areas (1.5 cm diameter) are located on the scalp in the hair recession area of the frontotemporal and vertex regions and will be marked with a red dot tattoo in the middle, as depicted. Edges will be marked as dots using a skin temporary marker.

To help relocate the tattoo dot the following distances should be documented:

- R: Distance between the tattoo and the middle of the right tragus
- L: Distance between the tattoo and the middle of the left tragus
- N: Distance between the tattoo and the tip of the nose.

Figure 3 Schematic picture of distance measurements

The minimal distance between treatment areas should be 5 cm.

Instructions for Application

Before clinical examination of the subject's treatment areas and subsequent application of FOL-005, the treatment areas will be cleansed by the investigator or trial personnel using a standard skin disinfectant.

The application of IP should be performed according to the following instructions:

- 1. Inject 50 µl to the treatment area according to the subject's specific randomisation list. Care should be taken to avoid injections at the very same spot on every visit.
- 2. Discard injection device.
- 3. Document injection.

This procedure is repeated for each treatment area.

9.1.2 Identity of Investigational Products

The active ingredient, FOL-005, is a chemically synthesised 15 amino acid peptide, which is based on an endogenous part of osteopontin. The sequence is H-Val-Asp-Thr-Tyr-Asp-Gly-Asp-Ile-Ser-Val-Val-Tyr-Gly- Leu-Arg. Each vial of the IP FOL-005, solution for injection contains 9 mL, 10 μ g/mL of FOL-005. It further contains sodium chloride, sodium hydrogen phosphate, hydrogen chloride, sodium hydroxide and purified water. The placebo product contains diluent only and is identical in appearance to the active product.

9.1.3 Packaging and Labelling of Investigational Products

FOL-005, 10 µg/mL solution for injection, is manufactured and released for the trial by Recipharm Pharmaceutical Development AB, Solna, Sweden.

All manufacturing is performed in accordance with current Good Manufacturing Practice (cGMP).

The labelling of FOL-005, solution for injection, the diluent and the dilution vials will be according to §5, GCP-V.

9.1.4 Storage and Handling of Investigational Products

The FOL-005 solution for injection must be stored in a freezer at a temperature of $<-20^{\circ}$ C. The temperature of the freezer will be logged.

The IP will be stored at the trial site as required by local regulations and laws for the participating site.

The IP, FOL-005, solution for injection will be thawed and reconstituted by dilution with isotonic phosphate buffer pH 7.4 into the following concentrations: 0.125, 0.5, 1.0, and 2.0 μ g/mL, as described in the study specific IP dilution manual. A schematic overview of the IMP dilution manual is found in Appendix 1. The handling of placebo is also described in the study specific dilution manual. Lab personnel not otherwise involved in assessment procedures will handle the preparation of vials.

9.2 Method of Assigning Treatment areas

Two of the 5 investigational treatments will be randomly assigned to the 2 treatment areas 1 and 2 according to the randomisation list for each subject. The treatment areas 1 and 2 will receive the same treatment throughout the trial period.

9.3 Selection of Doses in the Trial

The rationale for the choice of dose in the present trial is based on previous results from the phase I/IIa trial FCS-001

In FCS-001 the subjects were dosed twice or three times per week at four individual areas of the thighs with injections of 50 μ L resulting in 0.005 to 0.250 μ g of FOL-005. The maximum efficacy measured both as increase in hair density as well as in percentage of responders, was found at 0.025 μ g and the effect was more prominent after three administration times per week as compared to two times per week. FOL-005 was well tolerated at all tested doses and local tolerability AEs due to the injection procedure contributed to the majority of the reported events. Moreover, there was no detectable systemic absorption of FOL-005 at either of the doses.

In the present study 50 μ L of FOL-005 will be injected into two separate areas on the scalp. The scalp has a higher density of hair follicles than the thighs and the hair cycle intervals generally have a longer duration on the head, Therefore, it cannot be ruled out that the hair follicle on the scalp responds different to FOL-005 than hair follicles on the thighs The doses strengths in the present trial have therefore been selected to cover a range below and over the optimal dose strength identified in FCS-001, i.e. 0.025 μ g. The selected doses are 0.00625, 0.025, 0.050 and 0.10 μ g and each subject will receive different doses at the two separate areas, or one dose and placebo. The total maximal dose given to one individual subject in this trial - 0.150 μ g for the subjects receiving the 0.050 and 0.100 μ g doses - is well below the maximum dose given in the previous trial where each subject received four active doses, a total of 0.405 μ g at each occasion.

Based on clinical safety data from the previous study and the selection of doses in the present study, it is assumed that this design provides a minimized potential risk and a high probability to estimate possible effects of FOL-005.

9.4 Selection and Timing of Dose for Each Subject

The dose regime in the study, 3 times per week, is selected based on the results in the phase I/IIa trial FCS-001 where the subjects were treated 2 or 3 times per week. The efficacy measured both as increase in hair density as well as in percentage of responders, was more prominent after administration three times per week as compared to two times per week. FOL-005 was well tolerated at all tested doses and there was no detectable systemic absorption of FOL-005 at either of the dosing regimens. Injection related AEs such as haematomas and erythema, were more frequent in the group treated 3 times per week as

compared to the group treated 2 times. This is considered to be a result of the injection procedure and not the active ingredient. No increase in systemic AEs was found with the more frequent dosing.

Detailed descriptions of the treatment regimen and instructions for application of the IP are given in Section 9.1.1.

Restrictions to follow during the treatment period are described in Section 9.8.1.

9.5 Blinding

This trial will be double-blinded, meaning that neither the subject nor the Investigator will know which treatment areas will receive which treatment (actives or placebo). The appearance of the IP does not differ between the placebo and the active treatments.

The treatment of the subject's treatment areas will be randomised as described in Section 9.2 and the subjects will receive a subject and random number.

In order to ensure the double blindness in the trial, dilution of the IP will be done according to the Study Specific Laboratory Manual (see Appendix 1), by persons not otherwise involved in the trial.

9.6 Randomisation

Each randomised subject will be treated with 2 of the 5 trial treatments on the two treatment areas on the scalp. The two treatment areas (1 and 2) will be symmetrical placed on the scalp (see figure 2)

Thus, the subject will be randomised to receive any of the following 10 treatment combinations:

A:	٠	FOL-005 placebo:
	•	FOL-005 0.00625 µg:
В	٠	FOL-005 placebo:
	•	FOL-005 0.025 µg:
С	٠	FOL-005 placebo:
	•	FOL-005 0.050 µg:
D	٠	FOL-005 placebo:
	•	FOL-005 0.100 µg:
E	٠	FOL-005 0.00625 µg:
	•	FOL-005 0.025 µg:
F	٠	FOL-005 0.00625 µg:
	•	FOL-005 0.050 µg:
G	٠	FOL-005 0.00625 µg:
	•	FOL-005 0.100 µg:
Н	٠	FOL-005 0.025 µg
	•	FOL-005 0.050 µa:
		· · · · · · · · · · · · · · · · · · ·

•	FOL-005 0.025 µg
•	FOL-005 0.100 µg:
J •	FOL-005 0.050 µg:
•	FOL-005 0.025 µg

Each of these 10 combinations may be allocated in two ways: First treatment on area 1 and second treatment on area 2 or vice visa.

The total allocation ratio of treatments will be 5:5:5:5:4 where 4 depicts placebo.

In general, computer generated randomisation lists will be created containing one randomisation scheme per subject.

Upon signature of informed consent (screening period) each subject receives a 5-digit patient identification number, which is composed of:

Digits 1 and 2: trial center (01, 02, 03, etc.)

Digits 3, 4 and 5: individual screening number within the center (consecutively in the order of screening within the center: 001, 002, etc.)

Subjects who are eligible for enrollment into the trial will obtain a random number (501, 502, 503, etc.) The random number will not be reused if a subject discontinues the trial.

Subjects discontinued from the trial for IMP-unrelated reasons with treatment for less than 4 weeks will be replaced (see section 7.1). The replacement subject will receive the same treatments as the discontinued subject. The original randomization number will be replaced by a new randomization number generated by the last two digits of the original number preceded by 6 (e.g. original random number is 553; replacement random number is 653).

In order to further avoid bias of the results, the trial biostatistician will also be blinded and the preparation of the randomisation lists and envelopes are therefore performed by psy consult scientific services, Frankfurt, Germany, not directly involved in the study.

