- FOL-005 0.025 µg, or
- FOL-005 0.050 µg, or
- FOL-005 0.100 µg, or
- FOL-005 placebo.

Each subject will receive 2 trial treatments. The trial treatments will be randomised and a subject can receive any combination of the above 5 trial treatments except two of the same treatment. The expected duration of participation in the trial will be maximum 87 days for each subject.

Figure 1 Trial Design

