12.1.11 Other Safety Assessments

Physical Examination

Physical examination will be presented in a shift table. The shift table will show the number of subjects who changed (compared to visit 1) from "normal" or "abnormal" at baseline to "normal" or "abnormal" at each time of assessment.

Vital Signs

Vital signs will be summarised by treatment combination, together with changes from baseline, by visit.

Laboratory Safety Assessments

For laboratory data, summary statistics will be produced for observed values and for changes from baseline to each visit. In addition, the number of abnormal and clinically significant observations will be tabulated for each treatment combination by visit. Abnormal values will be flagged in listings.

Shift tables will show the number of subjects who changed from below, within or above the reference range at baseline to below, within or above the reference range at each time of assessment.

For laboratory values which are below the limit of quantification, the value corresponding to the limit of quantification will be used when summarising data (e.g. if the result is <x.x then the value x.x will be used in the statistical analysis).

Local Tolerance Assessments

Local tolerance assessments will be summarised by dose administered to the respective treatment areas.

12.2 **Determination of Sample Size**

The change from baseline until end of the treatment period (delta) is the primary efficacy endpoint and the base for the sample size estimation.

The expected standard deviation for delta is 23.0 based on data published by Olsen EA et. al [12]. The expected change in hair density from baseline is 8 % which is 13.6 hairs/cm² assuming the baseline hair density is 170 hairs/cm².

Using a statistical power of 80 % and a two-sided significance level on 5 % the number of fully evaluable subject on the dose of interest is 23. Assuming a dropout rate of 10 % results in a need to include 26 subjects whom all are given the dose of interest.

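### Section 9.6 announces 10 treatment combinations but lists nine different ones: J repeats H, and the 0.050/0.100 µg pair is missing

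*Combined protocol and SAP*

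**What the plan says.** Section 9.6 (Randomisation) states that "the subject will be randomised to receive any of the following 10 treatment combinations" and sets them out as entries A to J. It adds: "Each of these 10 combinations may be allocated in two ways", meaning that either member of a pair may go on area 1. The overall ratio is fixed: "The total allocation ratio of treatments will be 5:5:5:5:4 where 4 depicts placebo".

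Three other sections describe the same assignment:

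- Section 7.1: "a subject can receive any combination of the above 5 trial treatments except two of the same treatment".
- Section 9.2: "Two of the 5 investigational treatments will be randomly assigned to the 2 treatment areas 1 and 2", following the randomisation list.
- Section 9.3: the largest total dose in one subject is put at 0.150 µg, "for the subjects receiving the 0.050 and 0.100" µg doses.

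Section 12.1.11 uses the combinations as reporting groups. "Vital signs will be summarised by treatment combination, together with changes from baseline, by visit", and for laboratory data "the number of abnormal and clinically significant observations will be tabulated for each treatment combination by visit".

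**The concern.** The list follows a clear pattern: placebo with each dose (A to D), then 0.00625 µg with each higher dose (E to G), then 0.025 µg with each higher dose (H and the next entry, I). The only pair left is 0.050 with 0.100 µg. Entry J instead prints 0.050 with 0.025 µg, which is H in reverse order.

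Section 9.6 is where the protocol lists the combinations to be randomised. The same section gives preparation of the randomisation lists to an outside provider and keeps the trial biostatistician blinded, so the blinded team would not readily notice an absent pair. If the printed list were executed:

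- no subject would receive the highest combined dose that Section 9.3 describes;
- the vital-sign and abnormal-laboratory tables by combination would lack the highest-exposure group;
- if the printed letters were used as table groups, one pair would appear twice;
- the pairing of placebo with the active doses would be restricted in a way the protocol nowhere asks for.

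**Working it through.** **The announced number.** Two different treatments out of five give 5 × 4 / 2 = 10 unordered pairs, so 10 is the right target.

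**The printed list.** Combined dose is the sum of the two active amounts per occasion, in µg. The entry between H and J is called I.

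| Entry | Pair (µg) | Combined dose |
|---|---|---|
| A | placebo / 0.00625 | 0.00625 |
| B | placebo / 0.025 | 0.025 |
| C | placebo / 0.050 | 0.050 |
| D | placebo / 0.100 | 0.100 |
| E | 0.00625 / 0.025 | 0.03125 |
| F | 0.00625 / 0.050 | 0.05625 |
| G | 0.00625 / 0.100 | 0.10625 |
| H | 0.025 / 0.050 | 0.075 |
| I | 0.025 / 0.100 | 0.125 |
| J as printed | 0.050 / 0.025 | 0.075 |
| J corrected | 0.050 / 0.100 | 0.150 |

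Placement order does not separate J from H, because Section 9.6 already covers both orders within each combination. There are therefore nine different pairs, and the only absent one is 0.050/0.100 µg.

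**Appearances across A to J as printed.** Placebo 4, 0.00625 µg 4, 0.025 µg 5, 0.050 µg 4, 0.100 µg 3. A complete list has 4 of each.

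**Highest combined dose.** Section 9.3 gives 0.050 + 0.100 = 0.150 µg. The printed list reaches 0.025 + 0.100 = 0.125 µg (pair I). The drop is 1 − 0.125/0.150 = 17%. Both are below the 0.405 µg per occasion that Section 9.3 reports for the previous trial.

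**Effect on pair counts at the stated ratio.** There are 60 subjects and 120 areas. The ratio 5:5:5:5:4 sums to 24 and 120/24 = 5, which gives 25 areas per active dose and 20 for placebo. Let each letter stand for its number of subjects, with J the corrected pair:

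- placebo: A + B + C + D = 20
- 0.00625 µg: A + E + F + G = 25
- 0.025 µg: B + E + H + I = 25
- 0.050 µg: C + F + H + J = 25
- 0.100 µg: D + G + I + J = 25

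Adding the second and third lines and subtracting the fourth and fifth gives A + B + 2E = C + D + 2J. Substituting A + B = 20 − (C + D):

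J = E + 10 − (C + D).

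On the printed list nobody receives 0.050/0.100 µg, so J = 0 and

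E = C + D − 10.

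Taking the printed H and J as one pair, an enumeration found 14,201 whole-number solutions, all satisfying this equation. Of these, 6,126 use all nine pairs. In those E is at least 1, so C + D is at least 11 and A + B at most 9. If each placebo pair is given 5 subjects (an assumption), E = 5 + 5 − 10 = 0 and pair E disappears. With the corrected list, the same 5 per placebo pair requires only J = E.

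**The case against.** The strongest reply is that the protocol resolves the slip itself. Section 7.1 allows any two different treatments, Section 9.3 names subjects on 0.050 and 0.100 µg, ten is the right number of pairs, and the pattern of the list leaves J only one possible content. A careful list provider would probably read it correctly. The provider must also set the subject counts per pair separately, since equal use of ten pairs (6 subjects each) would give 24 areas per treatment rather than 25 and 20. That step might expose the duplicate.

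The consequences can also be called small. The primary analysis in Section 12.1.5 is a signed-rank test against zero within each dose, which does not depend on how doses are paired. Local tolerance is summarised by the dose given at the area, not by combination. Section 9.3 reports no detectable systemic absorption in the previous trial, and a lower maximum dose creates no new risk. Nor does Section 9.2 strictly require every pair to occur.

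Most of this stands. The intent is clear, there is no effect on power or the primary test if the ratio is kept, no safety hazard arises, and the firm conflicts are with Sections 7.1 and 9.3 rather than 9.2. What it does not remove is that the section specifying the randomisation prints the wrong set. A reader of Section 9.6 alone would not see that a pair is missing, and an error carried into the generated list could not be repaired after dosing. The restriction on pair counts applies only if the list is executed as printed at the exact ratio, but in that case it cannot be avoided.

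**Conclusion.** The concern holds: Section 9.6 is wrong as written and should be fixed. Ten combinations are announced and nine different ones listed; J duplicates H, and 0.050/0.100 µg is absent, contrary to Sections 7.1 and 9.3. It reads as a one-line error in entry J.

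If executed literally, it would cut the highest combined dose from 0.150 to 0.125 µg, remove the highest-exposure group from the by-combination vital-sign and abnormal-laboratory tables, and tie the placebo pairings to E = C + D − 10. These consequences depend on the generated list following the printed one, which the documents do not allow anyone to check; the last also assumes that 5:5:5:5:4 is met exactly with 60 subjects. No loss of power is claimed.

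**What to change.** Change entry J in Section 9.6 to 0.050/0.100 µg. Ask the list provider to confirm that the generated list contains all ten different pairs at the 5:5:5:5:4 ratio; this can be done without unblinding the trial team.

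Optionally, print the number of subjects per pair. One set that works is A, B, C and D 5 each; E and J 6 each; F, G, H and I 7 each:

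- total: 4 × 5 + 2 × 6 + 4 × 7 = 60 subjects
- placebo: 5 + 5 + 5 + 5 = 20 areas
- 0.00625 µg (A, E, F, G): 5 + 6 + 7 + 7 = 25
- 0.025 µg (B, E, H, I): 5 + 6 + 7 + 7 = 25
- 0.050 µg (C, F, H, J): 5 + 7 + 7 + 6 = 25
- 0.100 µg (D, G, I, J): 5 + 7 + 7 + 6 = 25

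The cost is one corrected entry and one confirmation, with no extra subjects and no change of ratio.

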9.7 Breaking the Randomisation Code

9.7.1 Un-blinding of Individual Subject Treatment

The trial sites will receive sealed envelopes containing a list of individual treatment codes. The envelopes will be kept by unblinded staff members at the trial site.

The unblinded staff will keep the envelopes in a secure, limited access location to prevent inadvertent breaking of the blind of the investigator. The double blindness must be maintained throughout the trial.

Suspected unexpected serious adverse reactions (SUSARs) will be unblinded for reporting to regulatory agencies and ethics committees. The pharmacovigilance team at FGK Clinical Research GmbH, Munich, Germany will be supplied with sealed envelopes of the randomization list to break the trial blind as required for regulatory reporting purposes. However, the investigator, sponsor, and blinded trial team will be kept blinded to treatment allocation. The information with regards to unblinding will be stored in a secure environment accessible only to pharmacovigilance team.

If the code has been broken for a subject, the subject will be withdrawn from the trial and procedures accompanying withdrawal are to be performed.

9.8 **Prior and Concomitant Therapy**

The use of prior medication used up to 4 weeks before study start and all concomitant medication (including Over the Counter and herbal medicines) by the subject will be recorded in the appropriate section of the eCRF up to the End of Trial Visit.

Medication, which is considered necessary for the subject's safety and well-being, may be given at the discretion of the Investigator. However, concomitant medication administered during the trial may lead to withdrawal of the subject from the trial (see Section 8.7) or subsequent exclusion form the PP analysis population if considered to be compromising the trial outcome.

9.8.1 Disallowed Concomitant Therapy and Procedures

The following treatments and/or procedures are prohibited during the trial:

- Prolonged UV exposition and UV tanning beds; subjects are advised to wear hats/caps while outside
- Sauna will not be permitted during the trial
- Use of any topical drug on the treatment area(s) except for subject's usual shampoo and hair care/cosmetic products as long as they do not claim to increase hair growth
- Use of any washes using alcohol, vinegar or other astringents, including peeling agents on the treatment areas
- Hair removal on skin treatment areas, e.g. waxing and shaving

The following should be avoided during the trial:

- More than once per day bathing/swimming
- Normal washing/showering of the head / scalp is allowed but a 2 hour free interval before or after injection should be respected

9.9 **Treatment Compliance**

Application of IP in the treatment areas will be performed only at the trial centre by qualified medical staff of the trial team. Compliance of the subject regarding concomitant therapies and the use of cosmetics in the treatment areas will be documented throughout the trial.

9.10 **Drug Accountability**

All IP supplied for this trial must be stored in a secure place. The Investigator or designated personnel at the trial site will keep a record of the inventory and dispensing of all IP. The Investigator is responsible for the drug accountability.

The monitor will perform a final drug accountability at the site before the used IP can be destroyed or shipped back to Sponsor (unused IP).

Study drug accountability, i.e., documentation of delivery, inventory, and return of IP will be maintained. Forms for documentation of the dilution procedures will be provided with the study specific IMP dilution manual.

